7.4.4. Second Injection Inclusion Criteria (Part II Patients Only)

To be eligible to receive the second injection during the open-label phase, patients must fulfill the following criteria:

- 1. Completed the double-blind phase of the study through Week 12
- 2. No major safety concerns during the initial dose period (including allergic reaction to initial dose of study medication) as assessed by the Investigator and patient
- 3. Clinically indicated to receive FX006, in the opinion of the Investigator and patient
- 4. WOMAC A (pain) score of ≥ 3 (0-10 NRS)
- 5. Compliant with study procedures and visit schedules up to the open-label injection with FX006 and the willingness and ability to continue to comply for additional 12 weeks after the second injection
- 6. Willingness to continue abstaining from use of protocol-restricted medications during the study (Refer to Section 7.6.2)

CONFIDENTIAL Page 37 of 72

7.4.5. Second Injection Exclusion Criteria (Part II Patients Only)

Patients fulfilling at least one of the following criteria may not be included in OLE phase of the study:

- 1. Clinical signs and symptoms of active hip infection or crystal disease of the index hip
- 2. Received a non-protocol specified IA intervention (IA injection, IA aspiration, etc.) in index hip during study participation
- 3. Use of immunomodulators, immunosuppressives, or chemotherapeutic agents during study participation
- 4. Received a live (e.g., MMR vaccine, chicken pox vaccine, rotavirus vaccine) or live-attenuated (e.g., FluMist, Zostavax) vaccine during study participation
- 5. Use of any other investigational drug, device or biologic during study participation
- 6. Any bacterial or viral infection requiring parenteral antibiotics within 4 weeks or oral antibiotics within 2 weeks of second injection
- 7. Skin breakdown at the hip where the injection would take place
- 8. Women who are pregnant or nursing or plan to become pregnant during the study; men who plan to conceive during the study
- 9. Women of child-bearing potential (not surgically sterile or post-menopausal for at least 1 year as documented in medical history) not using a highly effective method of contraception [abstinence; oral, injected or implanted hormonal methods of contraception; intrauterine device or intrauterine system; condom or occlusive cap (diaphragm or cervical/vault caps) with spermicidal foam/gel/film/cream/suppository, or male sterilization (vasectomy)]
- 10. Any other clinically significant acute or chronic medical conditions (e.g., bleeding disorder) that, in the judgment of the Investigator, would preclude the use of an IA corticosteroid or that could compromise patient safety

7.4.6. Removal of Patients from Therapy or Assessments

Each randomized and treated patient in Part I and the Part II double blind phase of the study receives study medication as a single administration. Therefore, discontinuation from treatment is not applicable. Patients may be discontinued from study follow-up as detailed below. Data collected from discontinued patients will be included in the clinical study report. Patients who discontinue the study may be replaced at the discretion of the Sponsor.

Withdrawal of Consent

Each patient will be informed of his/her right to withdraw from the study at any time for any reason and without prejudice to alternative treatment. If a patient decides to withdraw from the study, effectively withdrawing his/her informed consent, the Principal Investigator will:

- 1. document in patient's source their withdrawal of consent and reason for withdrawing from the study,
- 2. assess the patient's clinical condition and take appropriate therapeutic measures if necessary,

CONFIDENTIAL Page 38 of 72

- 3. attempt to complete the study assessments defined for the Final/Early Termination Visit, and
- 4. determine whether the patient is willing to be contacted on a monthly basis (via phone or in person) to follow ongoing or new AEs (including concomitant medication(s) associated with an AE) through the patient's scheduled final visit

Discontinuation of Follow-up by Investigator

The Principal Investigator may discontinue the patient for safety and poor compliance to study procedures. The Principal Investigator should contact the Medical Monitor prior to discontinuing the patient.

Discontinuation of Follow-up by Sponsor

Patients participating in Part I of the study will return for follow up visits at Weeks 12, 16, 20, and 24 or up until the time of this amendment at which time they will be discontinued. The patients will be discontinued at the time of notification by the Investigator.

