5.2.6. Efficacy in Patients with Osteoarthritis of the Knee

Efficacy data from three studies provide substantial evidence supporting the effectiveness of 32 mg FX006 in the management of OA pain (Bodick et al, 2015; Conaghan et al, 2018a; Conaghan et al, 2018b). Results of the primary endpoint from the Phase 3, multi-center, adequate, and well-controlled trial showed that patients treated with 32 mg FX006 had a rapid, durable, and meaningful analgesic response that was statistically significantly better than placebo treated patients (P<0.0001). This finding was supported by a second smaller Phase 2b study, where a highly similar pattern of response to 32 mg FX006 was demonstrated.

Robustness of the primary outcome in the Phase 3 study was further supported by the internal consistency demonstrated in favor of 32 mg FX006 through secondary analyses utilizing the primary outcome data (average daily pain [ADP]) to evaluate durability and magnitude of response. These included least square mean (LSM) testing at each week and area under the

CONFIDENTIAL Page 25 of 72

effect curve (AUE) analyses for Weeks 1 through 12 and Weeks 1 through 24. Results demonstrated that the analgesic effect of 32 mg FX006 is significant at Week 1, increases through Week 7, and is sustained through at least Week 16. Responder analyses further suggested that FX006 provides clinically relevant improvement from Weeks 1 through 16 relative to placebo.

Analyses utilizing data collected from other instruments or measures, i.e., Western Ontario and McMaster Universities Osteoarthritis Index (WOMAC), Patients' Global Impression of Change (PGIC), Clinical Global Impression of Change (CGIC), and Knee injury and Osteoarthritis Outcome Score (KOOS) Quality of Life (QOL), provided additional insight into effects on pain relief as well as physical function and global well-being. At 32 mg, FX006 provides clinically relevant improvement relative to placebo through Week 12 for WOMAC and KOOS QOL and through at least Week 16 for PGIC and CGIC. Additionally, significant reduction of rescue medication utilization in patients treated with 32 mg FX006 is of potential important clinical consequence and adds a meaningful element to the overall effectiveness profile of 32 mg FX006. Collectively, these results provide substantial evidence to support 32 mg FX006 as an effective therapy for the management of OA knee pain.

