9.2.1. Analysis Populations

The following analysis populations are planned for each part of this study as follows:

- Full Analysis Set (FAS) Population: All patients who received study drug. The FAS population will be used to examine efficacy endpoints for the double-blind phase of the study
- Safety Population: All subjects who received at least one dose of study drug. The Safety Population will be used to assess safety and tolerability
- Second Injection Population (Part II only): All patients who received a second injection. The Second Injection Population will be used to examine efficacy endpoints in the openlabel extension phase of the study
- Per Protocol Population (Part II Only): All patients in the FAS population who completed the Week 12 visit with no major protocol deviations that may impact the evaluation of the primary efficacy endpoint based on blinded data prior to unblinding of the double-blind phase data.

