9.4.3. Efficacy Analyses

Primary Efficacy Analysis

The primary endpoint will be analyzed with a longitudinal mixed model for repeated measures (MMRM) with fixed effects for treatment group, study week, treatment-by-week interaction and Baseline score. Subject will be the random effect. Treatment differences from control will be estimated via least square means from the analysis model along with 95% confidence intervals, and associated 2-sided p-values. This model assumes missing at random and includes only observed data.

Secondary Efficacy Analyses

Key secondary endpoints will be assessed similarly to the primary endpoint. Multiplicity will be addressed by analyzing the key secondary endpoints sequentially in the order presented in the protocol, testing each endpoint at the nominal alpha=0.05, 2-sided level to ensure overall type I error control at the 2-sided 0.05 level.

Additional continuous secondary efficacy endpoints will also be assessed similarly to the primary endpoint, but are not part of the sequential testing approach. Categorical end points will be compared via chi-square or exact tests depending on incidence rates.

AUE will be calculated and comparisons of the AUE endpoints will be estimated from an Analysis of Covariance (ANCOVA) with model parameters for treatment and covariates of Baseline WOMAC A score and study site. Full details of the AUE analyses will be detailed in the SAP.

Efficacy Analyses For The Open-Label Extension Phase (Part II)

Exploratory efficacy endpoints for the open-label extension phase will be analyzed similarly to the primary and secondary endpoints, but separately for the time period prior to the second injection and the time period post the second injection. Time-to-event endpoints will be assessed via log-rank tests and results will be presented in Kaplan-Meier plots.

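### Section 7.4.6 lets the investigator end follow-up but, unless consent is withdrawn, asks for no further efficacy data, so Week 12 pain scores can be lost from patients who still consent

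*Protocol*

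**What the plan says.** Protocol 7.4.6 notes that patients in Part I and in the Part II double-blind phase receive a single administration. "Therefore, discontinuation from treatment is not applicable." What can be ended is follow-up, and three routes are given.

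- **Withdrawal of consent.** Four steps follow. Step 3 is to "attempt to complete the study assessments defined for the Final/Early Termination Visit, and" step 4 is to "determine whether the patient is willing to be contacted on a monthly basis (via phone or in person) to follow ongoing or new AEs".
- **Discontinuation by the investigator.** "The Principal Investigator may discontinue the patient for safety and poor compliance to study procedures." The one added condition is "The Principal Investigator should contact the Medical Monitor prior to discontinuing the patient." No assessment, visit or contact is listed.
- **Discontinuation by the sponsor.** This concerns Part I patients at the time of the amendment.

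SAP 4.2.7 describes discontinuation as leaving further assessments and visits. Protocol Table 7-2 has no early-termination column. The primary endpoint is change in WOMAC A at Week 12 (Protocol 9.2.3.1). On the primary model, Protocol 9.4.3 states: "This model assumes missing at random and includes only observed data." SAP 4.2.8 does not impute missing visits, and missing-data sensitivity analyses are optional (Protocol 9.2, SAP 4.10.9). The Part II Per Protocol population in Protocol 9.2.1 requires completion of the Week 12 visit with "no major protocol deviations that may impact the evaluation of the primary efficacy endpoint".

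**The concern.** With no treatment to stop, ending participation means ending data collection. The plan asks more of a patient who has withdrawn consent than of one who has not but whom the investigator has discontinued. For the second patient, following the plan as written produces no Week 12 WOMAC A.

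Losing a few scores at random would cost little. The worry is selection. If patients are removed for reasons tied to pain or analgesic use between visits, the missing scores are not a random sample of what the model predicts for them. If this differs by arm, the estimated difference moves. Some difference between arms is plausible: for the knee, Protocol 5.2.6 reports "significant reduction of rescue medication utilization in patients treated with 32 mg FX006". Data collected after a deviation can be set aside in a supportive analysis, whereas data never collected cannot be recovered.

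The stake lies mainly in Part II, since Part I is exploratory.

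**Working it through.** **Inputs.** Protocol 9.3.1 gives a difference of 0.65, SD 2.0, two-sided alpha 0.05, 90% power, 212 per arm as a minimum, about 220 per arm planned, and 6% early discontinuation. The first key secondary endpoint has difference 0.68 and SD 2.125. The documents do not say how many patients investigators would remove, how removals would split by arm, or how far removed patients would depart from the model's prediction. Values for these are assumptions.

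**Step 1: reproduce the plan's figures.**

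- Primary: n = 2 × (1.960 + 1.282)² × 2.0² / 0.65² = 199 per arm; 199 / (1 − 0.06) = 212.
- First key secondary: n = 2 × (1.960 + 1.282)² × 2.125² / 0.68² = 206 per arm; 206 / (1 − 0.06) = 220.

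Both stated figures are matched once the 6% is included. The allowance protects the number of evaluable patients; it does not address which patients are lost.

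**Step 2: power at the planned size.** Evaluable patients per arm are 220 × 0.94 = 206.8. SE = 2.0 × √(2 / 206.8) = 0.197. Power = Φ(0.65 / 0.197 − 1.960) = 91.1%. Expected loss alone does not harm the trial.

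**Step 3: shift from selective loss.** Let f be the share of an arm removed before Week 12, and g the amount by which removed patients' true Week 12 score would differ from the model's prediction under missing at random. With the same g in both arms, the shift in the treatment difference is (f placebo − f FX006) × g. Power after a shift b toward no effect is Φ((0.65 − b) / 0.197 − 1.960).

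| Assumption | f placebo / f FX006 | g | Shift | Share of 0.65 | Power |
|---|---|---|---|---|---|
| All of the 6% are such removals | 9% / 3% | 1 | 0.06 | 9% | 85% |
| All of the 6% are such removals | 9% / 3% | 2 | 0.12 | 18% | 77% |
| A third of losses are such removals | 3% / 1% | 1 | 0.02 | 3% | 89% |
| A third of losses are such removals | 3% / 1% | 2 | 0.04 | 6% | 87% |

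Here g is positive: removed patients would have been worse than predicted, more of them are on placebo, and the observed difference is too small. The sign reverses if they would have been better than predicted, for instance on prohibited analgesics, or if more were on FX006. With no true effect, a shift of 0.06 or 0.12 in favour of FX006 would raise the two-sided type I error from 5% to 6.1% or 9.4%. Equal removal and equal departure in both arms give a shift of zero.

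**Step 4: what full retention would recover.** If every Week 12 score were obtained, 220 per arm would be evaluable and power would be 92.6% against 91.1%. The precision gain is small; the benefit is mainly less exposure to bias.

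**The case against.** Several readings that a reader might infer go further than the documents allow.

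- **That removed patients leave safety follow-up.** They do not. Protocol 8.2 follows serious adverse events to resolution or withdrawal of consent, and 8.5 follows all adverse events to resolution or a stable outcome. What is unclear is scheduled detection of new events, because Section 8 monitors only to the end of participation.
- **That poor compliance means taking prohibited analgesics, or rescue within 48 hours of a visit.** The term is undefined. Protocol 7.4.2 and 7.4.4 list compliance with procedures and visits separately from abstaining from restricted medication. On that usage it may mean missed visits, where removal loses less that would otherwise have been obtained. The knee finding concerns rescue use overall, not use just before visits and not removals.
- **That the model ignores pain.** It contains baseline WOMAC A and all observed post-baseline scores (Protocol 9.4.3, SAP 4.10.1.1). Removal driven by pain already recorded is compatible with missing at random. Only unrecorded pain, or analgesic use outside the model, remains a concern.
- **That the 6% measures these removals.** It covers all early discontinuation, so the upper rows of the table are an extreme allocation.

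The Medical Monitor contact is also a real check, the clause is permissive, and only removals before Week 12 affect the primary endpoint. The SAP supplied covers Part I; the Part II SAP, which may plan missing-data sensitivity analyses, was not available.

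These points narrow the concern and lower its likely size. They do not fill the gap: 7.4.6 still requires no efficacy data from a consenting patient whom the investigator discontinues, and a sensitivity analysis cannot replace a score that could have been collected.

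**Conclusion.** The point holds in a limited form. As written, the plan can lose Week 12 WOMAC A from patients who have not withdrawn consent, in a trial with no treatment to discontinue during the double-blind phase. Bias requires that removal depend on something the recorded scores do not capture, and that its effect differ between arms. The direction cannot be predicted.

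The size is unknown. The illustrative shifts run from 0.02 to 0.12 points, with power between about 89% and 77%, and rest wholly on an assumed removal rate, split and departure. They do not show that the trial is biased or underpowered. Nor do the documents support the conclusion that compliance must be struck out as a ground for discontinuation: the gap is in data collection, and when a patient should be discontinued is not judged here. This is a cheap improvement, best made before Part II enrols.

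**What to change.** In Protocol 7.4.6, keep the investigator's discretion and the Medical Monitor contact, but separate ending study procedures from ending data collection. For any patient discontinued by the investigator who has not withdrawn consent:

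1. Apply the existing steps 3 and 4 (early-termination assessments, and asking whether monthly adverse event contact is acceptable).
2. Continue to seek the scheduled WOMAC through Week 12. An early-termination visit alone is not enough: if it were handled as unscheduled data, SAP 4.2.9 would map it at most to the nearest scheduled visit, so it would not necessarily give a Week 12 score.
3. Record the deviation, so that it can be considered for the Part II Per Protocol population on blinded review.

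The cost is protocol wording, and a few patients staying in visits already scheduled. One downside is that some retained scores will follow prohibited analgesic use, and the Per Protocol set does not remove them from the primary analysis. The Part II SAP should therefore say how such scores are handled, and should specify a missing-data sensitivity analysis, such as a delta-adjusted tipping point, for scores that remain missing.

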7.4.7. Screen Failures

Minimal data for patients who fail screening such as demographic information and the reason for screen failure will be collected.

Patients that fail to meet eligibility criteria may be re-screened with the approval of the Medical Monitor, the preferred method being a request through the General Log in EDC. The Medical Monitor will document the rationale for any re-screening decision.

Patients that are re-screened will be assigned a new screening number, re-consented, and will have screening assessments repeated if necessary.

7.5. Treatment Administered

7.5.1. Study Medication Treatment Arms

Investigational Medicinal Product Arm:

• FX006 – an extended release formulation of triamcinolone acetonide (TA) in 75:25 poly (lactic-co-glycolic) acid (PLGA) microspheres. Nominal 32 mg TA, IA administered as a single 5 mL injection into the index hip OA joint under fluoroscopy guidance per injection procedure.

Reference Compound:

• Normal saline, sodium chloride (0.9% NaCl) solution, IA, administered as a 5 mL injection into the index hip OA joint under fluoroscopy guidance per injection procedure.

7.5.2. Identity of Investigational Product(s)

FX006 is supplied as a sterile, white to off white powder in a single unit dose 5 mL vial with a butyl rubber stopper, aluminum seal and plastic cap. FX006 is reconstituted in diluent containing an isotonic, sterile aqueous solution of sodium chloride (NaCl; 0.9% w/w), carboxymethylcellulose sodium (CMC; 0.5% w/w) and polysorbate-80 (0.1% w/w) to form a

CONFIDENTIAL Page 39 of 72

suspension prior to IA injection. Diluent will be supplied as a sterile liquid in a 5 mL vial with a butyl rubber stopper, aluminum seal and plastic cap. FX006 will be reconstituted in 5.0 mL of diluent to form a suspension immediately prior to IA injection. FX006 will be administered as a single 5 mL IA injection.

7.5.3. Identity of Reference Compound

Normal saline (0.9% sodium chloride injection, USP, supplied as a 10 mL vial) is a sterile, nonpyrogenic, isotonic solution of sodium chloride and water for injection. Each mL contains sodium chloride 9 mg.

7.5.4. Receipt, Preparation, Dispensing and Storage

Study medication will be shipped to the site from the drug supply distribution center. Receipt and dispensation of study medication will be properly documented within the Drug Tracking Module. Any temperature excursions should be documented in the Drug Tracking Module and on specified documents for Sponsor assessment and authorization for continued use.

Dispensing, preparation and administration of investigational products occurs under the supervision of the Principal Investigator. The Principal Investigator may only delegate these activities in accordance with state licensing board requirements, and local institutional policies, and applicable law. Before delegating this activity, the Principal Investigator should also ensure that the delegate is trained on and understands the requirements of the protocol.

The packaged kits of FX006 will be stored in a secure area and will be stored refrigerated at 2 to 8 °C. Normal saline will be stored in a secure area at room temperature.

7.5.5. Packaging and Labeling of Study Medication

The study medication will be labeled in accordance with local guidelines, as applicable.

7.5.6. Return of Study Medication

All study medications (packaged kits/used and unused vials) will be returned to the drug supply distribution center and will be documented within the Drug Tracking module. Return of study medications will be properly documented.

7.5.7. Method of Assigning Patients to Treatment Groups

Eligible patients will be randomized within strata defined by Baseline Western Ontario and McMaster Universities Osteoarthritis Index (WOMAC) A (pain) (0-10 numeric ratings scale (NRS) average of Screening 2 and Day 1 as follows: 5.0 to < 6.0, 6.0 to < 7.0, and $\geq 7.0 \text{ to} 9.0$ (see Section 9 for details).

7.5.8. Blinding

The blinded-assessor technique will be used in this study in order to maintain double blind conditions. Key site staff roles are defined in Section 7.2 and a site specific blinding plan will be developed to ensure the blind is maintained throughout the duration of the study. Treatments will be prepared by an unblinded pharmacist/coordinator who has experience with the

CONFIDENTIAL Page 40 of 72

preparation of study medication and who has been properly trained by the Sponsor or designee. IA injections will be performed by an unblinded injector.

Overall unblinded team responsibilities are as follows:

- Will have no other contact with the patient and will not have any blinded roles on the study (the only exception is that the unblinded injector may be delegated the role of obtaining informed consent at the Screening visit)
- Will not share treatment assignments with the blinded assessor, the patient and other blinded study personnel and Sponsor personnel/representatives
- Will make every effort to maintain the blind (e.g., preparation of both study agents will include similar tapping actions, so both "sound" the same).

Detailed responsibilities for the unblinded site staff are as follows:

- Unblinded Pharmacist/Coordinator:
 - o Receives the randomization notification of the subject's study treatment
 - Dispenses the appropriate prepared study treatment and necessary materials for the injection
 - Completes the drug accountability logs
 - o Transports assigned treatment to the location where injection will take place
 - o Will remain with the patient and unblinded injector until the injection is completed
 - o Ensures the blind is maintained by following the site specific blinding plan to ensure the patient is unaware of the treatment assignment prepared for injection
 - Performs the study drug reconstitution
 - o Will ensure that the FX006 drug is re-suspended prior to injection
 - Will record details of study drug preparation, transport (if applicable) and administration.
 - Will, in collaboration with the Unblinded Injector as appropriate, record any product-related issues relating to reconstitution or administration of FX006 (e.g., inability to achieve an appropriate suspension, inability to administer the full dose due to clogging of the needle) and report the occurrence to the Unblinded Site Monitor, as detailed in the Pharmacy Binder.
 - Will, in collaboration with the Unblinded Injector, prepare a blinded written record of any clinical AE and report the event to the (blinded) Principal Investigator and the Blinded Study Coordinator who will enter the event in the EDC and assess, treat, and follow-up the patient as appropriate.
 - Will transport the used vials back to the drug storage location to be held until drug accountability is performed by the unblinded monitor.

Depending on site specific requirements, the unblinded pharmacist/coordinator may be split into two roles. Details will be specified in the site specific blinding plan

CONFIDENTIAL Page 41 of 72

- Unblinded Injector
 - Performs the study drug reconstitution (if not completed by the unblinded pharmacist/coordinator)
 - o Will ensure that the FX006 drug is re-suspended prior to injection
 - o Performs the aspiration and injection of the index hip using fluoroscopy in accordance with both their experience and the protocol-specified procedure.
 - o Will, in collaboration with the Unblinded Pharmacist/Coordinator, record any product-related issues relating to reconstitution or administration of FX006.
 - Will, if the patient experiences any clinical AE while in the procedure suite, provide prompt medical care, as appropriate, including requesting additional assistance. Patient safety is always paramount, but, if feasible, minor events should be handled without unblinding the blinded study team.
 - o Will prepare a blinded written record of the AE and report it to the blinded assessor, who will assess, treat, and follow-up with the patient as clinically appropriate

All other site and Sponsor personnel/representatives involved in the study at the site will be blinded with regard to the study medication being administered with the following Sponsor/representative exceptions:

- Unblinded monitor(s):
 - Responsible for unblinded site monitoring.
 - Will perform study drug accountability (used and unused vials)
 - Is the primary point-of-contact for the Unblinded site personnel in the event of any "product complaint" (e.g., difficulty reconstituting study drug, inability to inject complete dose of study drug)
 - Will report all product-related issues within 24 hours to the designated unblinded personnel at the Sponsor.
- Unblinded clinical manager:
 - o Responsible for oversight of unblinded site monitoring.
 - Will review unblinded monitoring visit reports and escalate unblinded site issues to unblinded Sponsor representative
- Unblinded Sponsor representative
 - o Point of escalation for unblinded team
 - Will address any product related issues
 - o Will escalate in a blinded manner to the blinded study team, if necessary
- Sponsor Regulatory and Pharmacovigilance personnel for safety assessment and reporting, if necessary

CONFIDENTIAL Page 42 of 72

Information regarding the treatment assignments will be kept securely by Sponsor or designee, per its standard operating procedures.

